### ***Investigational Plan***

This is an exploratory, single center, open label, parallel-dose, and prospective study of BR55 CEUS for characterization of solid pancreatic lesions in subjects with suspected PDAC using transabdominal US. This study will be conducted in the US.

Approximately twenty-four (24) subjects with suspected PDAC and scheduled to undergo surgical resection or endoscopic ultrasound-guided fine needle biopsy (EUS-FNB) within 30 days (but not before 24 hours) after the transabdominal BR55 CEUS examination will be enrolled.

Subjects will be enrolled into 3 dose groups starting with the lowest dose group as follows:

- Dose group 0.03mL/kg
- Dose group 0.05mL/kg
- Dose group 0.08mL/kg

A maximum of 8 patients will be enrolled in each dose group according to the following methodology.

Enrollment into the next higher dose group will be based on the technical adequacy of the ultrasound acquisitions, as determined by a consensus medical review of images acquired in the first 4 subjects of the preceding dose group. Technical inadequacy of the ultrasound acquisitions will be determined in accordance with, but not limited to the following criteria:

- absent or insufficient contrast enhancement during the wash-in phase
- absent or insufficient contrast enhancement in subsequent image acquisitions (i.e. after the wash-in phase)
- lack of visualization of the target lesion in the post-contrast image acquisitions

Efficacy evaluations will be made on the US images that are acquired adequately. The Investigator will record the size, location and echogenicity of the lesion for UEUS. After BR55 is administered, the CEUS images will be evaluated for contrast enhancement using a semi-quantitative scale and a quantitative measurement of the SI in the target lesion vs. surrounding pancreatic tissue.

The final cancer diagnosis will be obtained for all subjects by histopathology.

Safety will be evaluated in this study by performing physical exams, collecting concomitant medications and the monitoring of adverse events, vital signs, electrocardiograms, laboratory tests and pulse oximetry.

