**Final Version**  
**10 April 2019**

---

Three different doses of BR55 will be evaluated: 0.03, 0.05 and 0.08 mL/kg. A total of eight (8) subjects will be enrolled sequentially into each dose group starting at 0.3 ml/kg.

A maximum of 8 patients will be enrolled in each dose group according to the following methodology.

Enrollment into the next higher dose group will occur either after a total of 8 subjects complete enrollment, or the first 4 subjects enrolled in the previous dose group have CEUS images that are not technically adequate based on consensus medical review by PI & Bracco. Reasons for technical inadequacy will be recorded on the CRF and may include the following:

- absent or insufficient contrast enhancement during the wash-in phase
- absent or insufficient contrast enhancement in subsequent image acquisitions (i.e. after the wash-in phase);
- lack of visualization of the target lesion in the post-contrast image acquisitions

In each subject, the administration of BR55 will be followed by a 10 mL 0.9% saline flush.

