**Contrast Enhanced (CEUS) Ultrasound Assessment**

The investigator should indicate in the Case Report Form whether or not contrast enhancement was seen in the target lesion during the 60 second wash-in phase. Also the investigator should record the degree of specific (e.g., BR55-VEGFR2 binding) enhancement seen according to the 3-point semi-quantitative visual scale outlined below.

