***Statistical Methods******Analysis Population***

Safety analysis population will consist of all subjects who are dosed.

Efficacy analysis population will include the data from all subjects who are dosed and have efficacy data available.

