***Efficacy Analysis*****General**

Efficacy analysis will include the data from all evaluable subjects who are dosed and have efficacy data available. The results will be presented for each dose group, if applicable. Except as noted, the statistical tests will be two-sided at the 0.05 level of significance with 95% confidence limit.

**Characterization of Pancreatic Lesions – by BR55 CEUS Visual Score Using  
Histopathology as the Truth Standard (TS)**

The objective of this study is to determine the ability of BR55 CEUS to characterize pancreatic lesions in subjects with suspected PDAC on the basis of a visual score (semi quantitative visual assessment of BR55 enhancement) using histopathology as the TS.

CEUS images of the pancreas will be assessed by the investigator as 3-point scale for contrast enhancement of BR55 (none, weak enhancement, and strong enhancement), while TS assessment result will be classified as malignant if cancer is found or as benign if no cancer is found. Frequency tables will be provided for BR55 enhancement scores by TS assessment results (malignant and benign).

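### Images judged inadequate, a class that includes absent enhancement, may be left out of efficacy, and no planned table shows adequacy or wash-in enhancement by dose

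*Combined protocol and SAP*

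**What the plan says.** **Doses and progression.** The Administration section states: "Three different doses of BR55 will be evaluated: 0.03, 0.05 and 0.08 mL/kg". The Investigational Plan says: "Enrollment into the next higher dose group will be based on the technical adequacy of the ultrasound acquisitions", judged on the first 4 subjects of the preceding group. Administration lets enrolment move on once a group reaches 8, or earlier if "the first 4 subjects enrolled in the previous dose group have CEUS images that are not technically adequate based on consensus medical review".

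**What counts as inadequate.** Both sections give the same open-ended list: missing or too little enhancement during wash-in, missing or too little enhancement afterwards, and a target lesion that cannot be seen after contrast. Administration adds: "Reasons for technical inadequacy will be recorded on the CRF and may include the following".

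**Who enters the efficacy analysis.** Three statements bear on this:

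- Investigational Plan: "Efficacy evaluations will be made on the US images that are acquired adequately".
- Analysis Population: "Efficacy analysis population will include the data from all subjects who are dosed and have efficacy data available".
- Efficacy Analysis, General: "Efficacy analysis will include the data from all evaluable subjects who are dosed and have efficacy data available". The added word *evaluable* is not defined.

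**What is scored and analysed.** The investigator records "whether or not contrast enhancement was seen in the target lesion during the 60 second wash-in phase" and a 3-point visual score, whose lowest level is no detectable stationary signal. The planned efficacy analyses are visual score by histopathology, signal intensity (SI) by histopathology (with optional ROC and logistic analyses), and Spearman correlations of SI with VEGFR2 and microvessel density. Results are to be shown per dose group where applicable. Data Handling promises subject listings of all collected data and counts of missing values in tables.

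**The concern.** Two of the three listed grounds for calling an exam inadequate concern enhancement, and enhancement is also what the visual score measures. If inadequate exams are left out of efficacy, some exams are removed because of a finding close to the lowest score. The remaining exams then look better than the dose performed, most of all at a dose that often fails to enhance.

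This affects the first objective as well as the reading by dose: the table of enhancement against histopathology would lose exams that belong in its no-enhancement row. The two recorded items that would reveal the loss, adequacy with its reasons and wash-in enhancement, have no planned summary, overall or by dose. The consensus review of adequacy is described only for the first 4 subjects of a group, so a comparable rating for subjects 5 to 8 is not assured.

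**Working it through.** **1. The plan's own figure.** Three groups of at most 8 give 3 × 8 = 24, which matches the stated total. The Sample Size section says that this number has no statistical basis, so there is no power calculation to check.

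**2. One exam under each section.** Take a dosed subject whose lesion is visible but shows no stationary signal after wash-in.

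| Section | Treatment of this exam |
|---|---|
| Investigational Plan | Meets an inadequacy criterion, so not evaluated for efficacy |
| Visual Assessment | Lowest visual score (no enhancement) |
| Analysis Population | Dosed with a score, so included |
| Efficacy Analysis, General | Depends on the meaning of *evaluable* |

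The sections give different answers for the same exam. An exam in which the lesion cannot be seen is a different case: it may have no usable score under any section.

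**3. Size of the effect.** The documents give no adequacy or enhancement rates, so the following are assumed. To keep lesion mix out of the illustration, take all lesions as malignant.

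- Dose A: 8 dosed, 2 strong scores, 6 inadequate for absent enhancement. Adequate images only: 2/2 = 100%. All dosed: 2/8 = 25%.
- Dose B: 8 dosed, 8 adequate, 6 strong. Either way: 6/8 = 75%.

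Among adequate images A is ahead of B (100% against 75%). Over all dosed subjects the order reverses (25% against 75%).

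**4. A group that stops at 4.** The text does not say whether all of the first 4 must be inadequate or whether one is enough. Let p be the true adequacy rate.

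- If all 4 must be inadequate, the probability of stopping at 4 is (1 − p)⁴:

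| p | Probability |
|---|---|
| 10% | 0.656 |
| 20% | 0.410 |
| 30% | 0.240 |
| 50% | 0.063 |
| 80% | 0.002 |

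A group stopped this way has 0 of 4 adequate exams and, on the Investigational Plan reading, contributes nothing to the efficacy tables. If both lower groups stop and the top group fills, the total is 4 + 4 + 8 = 16.

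- If one inadequate exam is enough, the probability is 1 − p⁴: 0.94 at p = 50% and 0.59 at p = 80%. A group stopped this way could still hold up to 3 adequate exams.

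**5. What an adequacy table could show.** Exact (Clopper-Pearson) 95% intervals:

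| Adequate/dosed | Rate | 95% interval |
|---|---|---|
| 0/4 | 0% | 0 to 60.2% |
| 2/8 | 25% | 3.2 to 65.1% |
| 4/8 | 50% | 15.7 to 84.3% |
| 6/8 | 75% | 34.9 to 96.8% |
| 8/8 | 100% | 63.1 to 100% |

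Fisher's exact two-sided p is 0.007 for 2/8 against 8/8 and 0.077 for 4/8 against 8/8. Only large differences would stand out.

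**6. Extra review work.** At most 3 × (8 − 4) = 12 image sets fall outside the first 4 of each group.

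**The case against.** A reader might infer that the doses cannot be compared at all, or that a failing dose is certain to vanish from the report. The documents support neither.

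- Results are to be presented by dose where applicable, and Data Handling provides listings of all collected data and missing-value counts. Much of adequacy and wash-in by dose could be tallied afterwards.
- Under the Analysis Population definition, a dose without enhancement stays in the tables as the lowest visual score, or as the no-signal SI category, so its failure shows.
- A group stopped early would be visible by its size, and its subjects remain in the safety and exposure summaries.
- Comparing doses is not among the listed objectives. The study is exploratory, and groups of at most 8 yield little precision.
- The restriction to adequately acquired images might refer only to acquisition quality, not to enhancement.

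Most of this stands, and it limits the point. Three things remain. A listing is not a planned summary, and it cannot supply a consensus rating that was never made for subjects 5 to 8. Missing counts need not separate an inadequate image from absent histology, and a subject outside the efficacy population need not be counted in an efficacy table at all. On the last objection, the restriction directly follows a list of inadequacy criteria that includes absent enhancement, so a reader would naturally apply that list.

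**Conclusion.** The concern holds in a limited form. The three statements on who enters the efficacy analysis disagree about an exam without enhancement. On the Investigational Plan reading, results by dose are selected on something close to the outcome, and a dose whose images fail can leave the efficacy tables. On the Analysis Population reading, an exam scored as no enhancement stays in. On either reading, no planned summary gives adequacy or wash-in enhancement by dose.

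The size cannot be taken from the documents. In the assumed example the choice of reading moves one dose from 25% to 100% and reverses the order of two doses; real data may show much less. The chance that a group stops at 4 and contributes nothing rests on an assumed adequacy rate and on the progression rule meaning all 4 subjects. This is an inexpensive improvement to an exploratory study. It does not show that the study cannot meet its objectives.

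**What to change.** 1. Reconcile the Investigational Plan, Analysis Population and Efficacy Analysis sections, and define *evaluable*, so that no dosed subject is removed from the efficacy tables because enhancement was absent.
2. Have the existing investigator-sponsor consensus review record adequacy (yes/no, with reason) for every dosed subject.
3. Add one descriptive table by dose with all dosed subjects as denominator: adequate yes/no, reason for inadequacy and wash-in enhancement yes/no, with exact 95% intervals.
4. Show the visual score by histopathology result and dose, with a row for inadequate images divided by reason and a column for histology not available. Both the adequate-only and the all-dosed denominators can then be read from the same table. Keeping the split by histopathology matters, because a pooled rate of strong enhancement would also vary with each group's mix of malignant and benign lesions.
5. State that comparisons between doses are descriptive, since the groups are sequential, non-randomised and at most 8 each.

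**Cost.** Plan wording, one new table, a modified frequency table, a small CRF change and at most 12 further image reviews by the existing reviewers. No added procedures for subjects. The intervals will be wide (4/8 gives about 16 to 84%), and the report should say so.

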### ***Methodology***

#### ***Study Schedule***

The Study Schedule is presented in Table B.

**Table B: Study Schedule**

Events	PRE-DOSE					BR55 inj.	POST-DOSE			
	Within 10d	Within 24h	Within 2h	-10 min	Immed. prior		+30 min	+1 h	+24 h	Up to 30 days
Written Informed Consenta	×	⇒								
Inclusion/Exclusion Criteria		×								
Demographics		×								
Medical Historyb		×								
Pregnancy testc		×								
Concomitant Medicationsd		×	⇒	⇒	⇒	⇒	⇒	⇒	⇒	×
Adverse Events Monitoringe		×	⇒	⇒	⇒	⇒	⇒	⇒	⇒	×
Physical Examination		×								×
Vital Signsf			×				×	×	×	
Pulse Oximetry				×	⇒	⇒	×			
Laboratory Evaluations		×								×
Weight assessment			×							
Electrocardiogram			×				×	×	×	
UEUS exam					×					
BR55 Administration						×				
BR55 CEUSg						×	×			
Surgical resection or EUS-FNB for suspected PDACh										×

a Obtain prior to implementation of any study procedure.b Includes disease related and general Medical History.c A serum βHCG pregnancy test to be performed in subjects of childbearing potential.d Record all medications (prescription and over-the-counter) taken within 24 hours prior to BR55 administration up through 24 hours after BR55 administratione Start monitoring from the time of signing Informed Consent up to 24 h post-dose. Only post-dose events will be tabulated as adverse events.f Includes systolic and diastolic blood pressure, and heart rateg Imaging will be performed as per instructions in the imaging manualh Surgical resection or EUS-FNB for suspected PDAC to be performed from 24 h up to 30 days post-dose.

*Written Informed Consent*

Obtain written Informed Consent from the subject prior to the implementation of study procedures required by the protocol. Give to the subject a copy of the signed and dated written informed consent form including any other written information regarding the study. Document Informed Consent process in detail in the source record at the site.

*Subject Evaluations*Demographics

Obtain demographic information on each subject (including; height, age, sex and race) and record on the Case Report Form.

Medical History

Obtain a complete medical history including disease related medical history and scheduled date for surgery for resection or endoscopic ultrasound-guided fine needle biopsy (EUS-FNB) of the suspected PDAC after the subject has signed the Informed Consent and within 24 hours prior to IP administration. Record the subject's medical history on the Medical History section of the Case Report Form.

Pregnancy Test

Exclude the possibility of subject's pregnancy:

- by testing (serum  $\beta$ HCG) within 24 hours prior to the start of investigational product administration;
- by surgical history (e.g., tubal ligation or hysterectomy);
- by post-menopausal status with a minimum of 1 year without menses

Concomitant Medications

Record all medications (prescription and over-the-counter) taken within 24 hours prior to IP administration in the Concomitant Medication section of the Case Report Form. Additionally, record newly prescribed pharmacological treatments in this section up through 24 hours post IP administration.

*Safety Assessment*Adverse Events

Monitor subjects for any untoward medical occurrences from the time of signing of Informed Consent through 24 hours post BR55 administration. Record all untoward medical events in the Adverse Event section of the CRF as specified in the protocol. Only post-dose untoward medical occurrences will be tabulated as adverse events.

All serious adverse events that occur during the study monitoring period are required to be collected regardless of the relationship to BR55 on the Serious Adverse Event Report (SAER) Form.

In addition, the investigator should report any serious adverse events that occur after the monitoring period that he/she believes may be related to the BR55 on the SAER Form.

### Physical Examination

Perform a physical examination within 24 hours prior to and at 24 hours after BR55 administration.

### Vital Signs

Collect the following vital signs within 2 hours pre-dose and approximately at 30 min, 1 hour and 24 hours after BR55 administration:

- Systolic blood pressure (mmHg)
- Diastolic blood pressure (mmHg)
- Heart rate (beats/minute)

### Pulse Oximetry

Pulse oximetry will be performed starting at 10 minutes prior to BR55 administration and continuing through 30 minutes after BR55 administration. During the monitoring period, any pathological change in pulse oximetry noted from pre-dose, including the timing in respect to BR55 administration, must be recorded on the CRF.

### Laboratory Evaluations

Collect blood and urine samples within 24 hours prior and at 24 hours post BR55 administration for evaluation of the analytes listed in the protocol.

A local laboratory will be utilized for analyzing and reporting laboratory results.

### Electrocardiograms

Acquire a 12-Lead ECG within 2 hours prior to and at approximately 30 min, 1 hour and 24 hours after BR55 administration. Attach a photocopy of the ECG report to the appropriate page of the Case Report Form.

ECG examinations will be performed locally and the ECG reports will be evaluated by a local cardiologist.

*Imaging Procedures*Ultrasound Equipment

The transabdominal UEUS and CEUS examinations will be performed with FDA-approved ultrasound equipment, commercially available for clinical applications. The BR55 CEUS evaluation of the pancreas should be performed with a contrast dedicated platform and equipped with a multi-frequency curved array transducer used for conventional transabdominal US examinations.

For standardization purposes, the same ultrasound system and transducer will be used for all subjects enrolled at the investigational site. Additionally, any technical interventions (including software release updates and periodic system maintenance) will be evaluated by the Sponsor in order to make sure the image quality is not affected.

A study dedicated preset will be installed on the selected ultrasound machine.

Ultrasound Image Acquisition

A detailed description of both the UEUS and BR55 CEUS acquisition protocols will be provided in a dedicated Imaging Manual.

The BR55 CEUS examination of the pancreas must be preceded by a standardized transabdominal UEUS examination of the pancreas to identify the focal target lesion. Oral fluid may be administered as needed to reduce shadowing gas in the stomach. Optimally, it should be possible to view the entire lesion within the field of view of the ultrasound transducer. UEUS will also serve to identify the optimal plane for imaging the target lesion after BR55 administration.

For the subsequent BR55 CEUS, to prevent microbubble destruction, the procedure should be performed in contrast mode using a low Mechanical Index.

Contrast inflow into the target lesion will be observed in the optimal imaging plane for approximately 60 seconds and using a low frame rate. Post-contrast images will be acquired at 2 minute time intervals, starting at 2 minutes and continue up to 30 minutes post BR55 administration, or until stationary enhancement in the lesion is no longer visible, whichever occurs first.

A copy of the DICOM images will be transferred to the Bracco Imaging Core Laboratory.

*Efficacy Evaluations*Unenhanced Ultrasound (UEUS) Assessment

The investigator will draw the area corresponding to the target lesion on the pancreas map in the Case Report Form, indicating the location of the lesion (head, neck, body or tail of the pancreas), the size in centimeters, and the echogenicity (i.e., hypoechoic, isoechoic, or hyperechoic).

**Contrast Enhanced (CEUS) Ultrasound Assessment**

The investigator should indicate in the Case Report Form whether or not contrast enhancement was seen in the target lesion during the 60 second wash-in phase. Also the investigator should record the degree of specific (e.g., BR55-VEGFR2 binding) enhancement seen according to the 3-point semi-quantitative visual scale outlined below.

**Visual Assessment of BR55 Enhancement of the Target Lesion**

BR55 contrast-enhanced images will be assessed by the investigator using the following semi-quantitative scale:

1. No enhancement: No focal targeted, stationary imaging signal is detectable.
2. Weak enhancement: Weak focal targeted imaging signal is detectable and considered as possibly stationary.
3. Strong enhancement: Well defined and strong focal targeted imaging signal is detectable and considered as definitely stationary.

**Quantitative Assessment of BR55 Enhancement**

A quantitative assessment of contrast enhancement with BR55 will be performed by drawing a region of interest (ROI) within the target lesion and measuring the SI within that ROI. The SI fold-change will be calculated as the ratio of the SI in the target lesion ROI to the SI in the surrounding tissue ROI. Further details on these measurements will be provided in the Imaging Manual.

***Diagnosis Confirmation*****Pathology and Immunohistochemistry Measurements for Pancreatic Lesions**

Standard protocols for collecting tissue samples from pancreas subjects undergoing surgery will be used as part of Standard of Care. Tissue sections from the suspected pancreatic lesion and normal tissue will be collected, macro dissected free of stroma and necrosis and processed using established standard clinical protocols. These samples will be used to correlate BR55 CEUS imaging signal with molecular markers of angiogenesis. For patients who will not undergo surgery after BR55 CEUS but will receive EUS-FNB, core tissue sample will be collected and used for correlation of CEUS imaging signal with IHC.

On the formalin fixed collected samples, the target lesion ROI or the core tissue sample will be assessed using standard histopathology and IHC analysis methods, including staining for the expression of VEGFR2 and CD31.

Histopathology measurements and IHC analysis will be described in detail in a separate dedicated Pathology Manual and performed on-site.

A copy of the pathology report will be collected to confirm the subject's diagnosis.

